4.3 Selection and Timing of Dose for Each Subject

The dosing regimen and schedule for Arm N and Arm N+I are detailed in Table 4.3-1 (Arm N), Table 4.3-2 (Arm N+I, Week 1-12), Table 4.3-3 (Arm N+I, Week 13 and following). Table 4.3-4 describes the dosing regimen for the C3 Cohort. Table 4.3-5 describes the dosing regimen for the C5 Cohort. Table 4.3-6 describes the dosing regimen for the C6 Cohort.

Table 4.3-1: Dosing Schedule for Arm N - Nivolumab Monotherapy

Every 4-Week Dosing	
480 mg Nivolumab	

Note: See for Section 3.1.4.1 for treatment duration

Table 4.3-2: Dosing Schedule for cStage 1/2 Arm N+I (Week 1-12) - Nivolumab + Ipilimumab Combination

Every 3 Week Dosing				
Study Part	Day 1 Dose 1/Week 1	Day 1 Dose 2/Week 4	Day 1 Dose 3/Week 7	Day 1 Dose 4/Week 10
Dose Escalation Phase Dose Level -1	0.3 mg/kg Nivolumab 1 mg/kg Ipilimumab	0.3 mg/kg Nivolumab 1 mg/kg Ipilimumab	0.3 mg/kg Nivolumab 1 mg/kg Ipilimumab	0.3 mg/kg Nivolumab 1 mg/kg Ipilimumab
Dose Escalation Phase Dose Level 1	1 mg/kg Nivolumab 1 mg/kg Ipilimumab	1 mg/kg Nivolumab 1 mg/kg Ipilimumab	1 mg/kg Nivolumab 1 mg/kg Ipilimumab	1 mg/kg Nivolumab 1 mg/kg Ipilimumab
Dose Escalation Phase Dose Level 2a	1 mg/kg Nivolumab 3 mg/kg Ipilimumab	1 mg/kg Nivolumab 3 mg/kg Ipilimumab	1 mg/kg Nivolumab 3 mg/kg Ipilimumab	1 mg/kg Nivolumab 3 mg/kg Ipilimumab
Dose Escalation Phase Dose Level 2b	3 mg/kg Nivolumab 1 mg/kg Ipilimumab	3 mg/kg Nivolumab 1 mg/kg Ipilimumab	3 mg/kg Nivolumab 1 mg/kg Ipilimumab	3 mg/kg Nivolumab 1 mg/kg Ipilimumab
Efficacy (cStage) ^a	(3 mg/kg Nivolumab + 1 mg/kg Ipilimumab) Q3W x4			3W x4

^a The staged phase uses maximum tolerable dose identified in escalation phase.

Table 4.3-3: Dosing Schedule for cStage 1/2 Arm N+I (Week 13 and following) - Nivolumab + Ipilimumab Combination

Every 4 Week Dosing	
480 mg Nivolumab	

Note: See for Section 3.1.4.1 for treatment duration

Table 4.3-4: Dosing Schedule for C3 Cohort: Nivolumab + Ipilimumab Combination

Every 2 or 6 Week Dosing			
Day 1 Week 1	Day 1, Week 3, 5, 7, 9 and every other week thereafter	Day 1 Week 7, 13, 19 and every 6 weeks thereafter*	
3 mg/kg Nivolumab	3 mg/kg nivolumab over 30 minutes		

Protocol Amendment No: 09

Table 4.3-4: Dosing Schedule for C3 Cohort: Nivolumab + Ipilimumab Combination

Every 2 or 6 Week Dosing			
Day 1 Week 1	Day 1, Week 3, 5, 7, 9 and every other week thereafter	Day 1 Week 7, 13, 19 and every 6 weeks thereafter*	
1 mg/kg Ipilimumab		1 mg/kg ipilimumab over 30 minutes	

Note: See for Section 3.1.4.1 for treatment duration

Nivolumab and Ipilimumab combination:

When both nivolumab and ipilimumab are to be administered on the same day, separate infusion bags and filters must be used for each infusion. Nivolumab is to be administered first. The nivolumab infusion must be promptly followed by a saline flush to clear the line of nivolumab before starting the ipilimumab infusion. The second infusion will always be ipilimumab and will start no sooner than 30 minutes after completion of the nivolumab infusion.

Dosing calculation based on weight:

The dosing calculations should be based on the body weight. If the subject's weight on the day of dosing differs by > 10% from the weight used to calculate the dose, the dose must be recalculated. The weight used to calculate the dose should always be the most recently recorded weight. All doses should be rounded to the nearest milligram. There will be no dose modifications allowed.

Body weight is determined as detailed in the Flow Chart/Time and Events Schedule of this protocol.

Dosing modifications:

There will be no dose modifications allowed for the management of toxicities of individual subjects.

For Q2W nivolumab dosing cycles, subjects may be dosed no less than 12 days between doses. For Q3W nivolumab dosing cycles, subjects may be dosed no less than 19 days between doses. For Q4W nivolumab dosing cycles, participants may be dosed no less than 25 days from the previous dose. For Q6W ipilimumab dosing cycles, participants may be dosed no less than 5 weeks from the previous dose. If dosing is delayed, both nivolumab and ipilimumab must be delayed together. If dosing is resumed after a delay, both nivolumab and ipilimumab must be resumed on the same day.

Table 4.3-5: Dosing Schedule for C5 Cohort: Nivolumab + BMS-986016 Combination		
Day 1 Week 1	Day 1, Week 3, 5, 7, 9 and every other week thereafter*	
240 mg nivolumab flat dose	240 mg nivolumab flat dose IV over 30 minutes	
160 mg BMS-986016	160 mg BMS986016 IV over 60 minutes	

Note: See for Section 3.1.4.1 for treatment duration

Table 4.3-6: Dosing Schedule for C6 Cohort: Nivolumab + Daratumumab Combination				
Drug	Dose	Frequency of administration	Route of administration	Duration
Nivolumab	240 mg flat dose	every 2 weeks starting on Week3	30 minute Intravenous (IV) infusion	Until progression, toxicity, or discontinuation from study
Nivolumab	480 mg flat dose	every 4 weeks starting on Week 25	30 minute Intravenous (IV) infusion	Until progression, toxicity, or discontinuation from study
Daratumumab	16 mg/kg	Every week (Weeks 1-8) Every 2 weeks (Weeks 9-24) Every 4 weeks (Starting on Week 25 and thereafter)	(IV) infusion Please refer to the daratumumab investigators brochure or pharmacy manual for infusion details.	Until progression, toxicity, or discontinuation from study

4.3.1 Re-initiation Dose Schedules

Subjects in the cohorts listed in Table 4.3.1-1 who met eligibility criteria for re-initiation of treatment (Section 3.1.4.8) will receive treatment as presented below:

Table 4.3.1-1: Treatment Schedules for Re-Initiation

Cohort	Treatment upon Re-initiation
mStage 1/2	Nivolumab 480 mg Q4W
cStage 1/2	Nivo 240 mg + Ipi 1 mg/kg Q3W for 4 doses, followed by Nivolumab 480 mg (Q4W)
C3 (1L)	Nivo 360mg Q3W + Ipi 1mg/kg Q6W
C5 (BMS-986016 /anti-LAG3)	Nivo 240mg Q2W + BMS-986016 (LAG3) 160mg Q2W

Note: "Re-initiation" relates to maximum clinical benefit participants.

Protocol Amendment No: 09

Treatment duration after re-initiation, inclusive of treatment beyond progression will be a maximum of 24 months.

4.3.2 Antiemetic Premedications

Antiemetic medications should not be routinely administered prior to dosing of drugs. See Section 4.3.7 for subsequent premedication recommendations following a study drug-related infusion reaction.

4.3.3 Dose Delay Criteria

Dose delay criteria apply for all drug-related adverse events (regardless of whether or not the event is attributed to nivolumab, ipilimumab, BMS-986016, daratumumab, or combinations). All study drugs must be delayed until treatment can resume (see Section 4.3.5). Treatment delays up to 6 weeks from the last dose are allowable. Study therapy should also be delayed in cases of confirmed or suspected severe acute respiratory syndrome coronavirus 2 (SARS-CoV-2) infection, regardless of the severity.

Nivolumab and ipilimumab administration should be delayed for the following:

- Any Grade ≥ 2 non-skin, drug-related adverse event, with the following exceptions:
 - Grade 2 drug-related fatigue or laboratory abnormalities do not require a treatment delay
- Any Grade 3 skin, drug-related adverse event
- Any Grade 3 drug-related laboratory abnormality, with the following exceptions for asymptomatic amylase or lipase, AST, ALT, or total bilirubin:
 - Grade 3 amylase or lipase abnormalities that are not associated with symptoms or clinical manifestations of pancreatitis do not require a dose delay.
 - If a subject has a baseline AST, ALT, or total bilirubin that is within normal limits, delay dosing for drug-related Grade ≥ 2 toxicity
 - If a subject has baseline AST, ALT, or total bilirubin within the Grade 1 toxicity range, delay dosing for drug-related Grade ≥ 3 toxicity

Nivolumab and BMS-986016 (C5 Cohort treatment) administration should be delayed for the following:

- Select drug-related AEs and drug-related laboratory abnormalities:
 - ≥ Grade 3 skin
 - ≥ Grade 1 pneumonitis
 - \geq Single grade increase shift in abnormality in AST, ALT, and total bilirubin
 - ≥ Grade 2 creatinine
 - ≥ Grade 2 diarrhea or colitis

- ≥ Grade 2 neurological AE
- Grade 4 amylase and/or lipase abnormalities regardless of symptoms or clinical manifestations
- ≥ 1x ULN troponin, hold dose and repeat troponin after 24 hours. All troponin elevations require a dose delay to allow for prompt cardiac evaluation. Following this evaluation, determination of further treatment will be based on the discretion of the PI.
- Any AE, laboratory abnormality, or concurrent illness that, in the judgment of the Investigator, warrants delaying the dose of study drug
- Grade 2 Myocarditis

Nivolumab and daratumumab (C6 Cohort treatment) administration should be delayed for the following:

- Grade 4 hematologic toxicity, except for Grade 4 lymphopenia
- Grade 3 or higher thrombocytopenia with bleeding
- Febrile neutropenia
- Neutropenia with infection, of any grade
- Grade 3 or higher non-hematologic toxicities with the following exceptions:
 - Grade 3 nausea that responds to antiemetic treatment within 7 days
 - Grade 3 vomiting that responds to antiemetic treatment within 7 days
 - Grade 3 diarrhea that responds to antidiarrheal treatment within 7 days
 - Grade 3 fatigue that was present at baseline or that lasts for < 7 days after the last administration of daratumumab
 - Grade 3 asthenia that was present at baseline or that lasts for < 7 days after the last administration of daratumumab

In Weeks 1 to 8, daratumumab doses that fall outside of the pre-specified window of -1 to ± 3 days must be skipped.

In Weeks 9 to 24, daratumumab dosing may be delayed for up to 1 week. If unable to administer within 1 week, then the dose should be skipped, and resumption of the daratumumab continues per the protocol defined schedule.

From Week 25 and beyond, the first dose (Week 25) can be delayed 21 days. Doses that fall outside the allowed window should be skipped.

During periods when daratumumab doses are skipped, daratumumab PK and immunogenicity samples should not be drawn.

Table 4.3.3-1: Daratumumab Dose Delay Guidance			dance
Week Frequency Dose Held Dosing Re-star		Dosing Re-start	
1-8	Weekly (q1wk)	> 3 days	next planned weekly dosing date
9-24	Biweekly (q2wks)	> 7 days	next planned biweekly dosing date
25+	Every 4 weeks (q4wks)	> 21 days	next planned every 4 weeks dosing date

Subjects experiencing a Grade 4 infusion reaction or their third Grade 3 infusion reaction related to daratumumab must permanently discontinue daratumumab. See Section 4.3.7 for additional details on the treatment of infusion reactions.

Any adverse event deemed to be related to daratumumab that requires a dose hold of more than 3 consecutive planned doses will result in permanent discontinuation of daratumumab. If a dose delay occurs, then pharmacokinetic and pharmacodynamic assessments should be performed on the actual day of study drug administration, not on the original scheduled administration day

Subjects whose dose are missing ≥ 3 consecutive planned doses of daratumumab for reasons other than toxicity should be withdrawn from study drug, unless, upon consultation with the sponsor and the review of safety and efficacy, continuation is agreed upon. Subjects who are withdrawn from daratumumab may continue to receive nivolumab.

• Any adverse event, laboratory abnormality, or intercurrent illness which, in the judgment of the investigator, warrants delaying the dose of study medication.

Because of the potential for immunotherapy-related AEs requiring early recognition and prompt intervention, management algorithms have been developed for suspected pulmonary toxicity, GI toxicity, hepatotoxicity, endocrinopathy, skin toxicity, neurological toxicity, and nephrotoxicity.

In order to standardize the management of adverse events for all subjects, treatment management algorithms recommended for utilization in this study are included in Appendix 1. Adverse event treatment management algorithms included in the nivolumab IB or ipilimumab IB might be considered for individual cases.

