- On-study laboratory assessments (after D1W1) should be drawn within 72 hours prior to dosing according to the schedule in Table 5.1-6.
- Herpes Zoster virus antiviral prophylaxis should be initiated within 1 week after starting daratumumab and continue during the Treatment Phase per institutional guidelines, and for 3 months following treatment discontinuation.
- Biomarker, PK, and immunogenicity samples will be obtained according to the schedules in Table 5.5.1-5 and Table 5.6.8-3.
- Study drug dosing may be delayed for toxicity for up to 6 weeks from the last dose. See Section 4.3.3.
- Administration of study drug continues until disease progression or until discontinuation of study therapy in subjects receiving study therapy beyond progression, discontinuation due to toxicity, withdrawal of consent, or the study ends.
- Patient-reported outcome(s) (PRO) instruments (EORTC QLQ-C30 & EQ-5D Questionnaires) will be completed following drug vial assignment but before first dose, and every 6 weeks through Week 24 and then at each dose, starting with Week 25 according to Table 5.1-6.
- This phase ends when the subject is discontinued from study therapy. Please refer to Section 3.5 and Section 4.3.6 for reasons for discontinuation.

3.1.4.8 Treatment Options Upon Progression after Treatment Discontinuation At Maximum Clinical Benefit

Subjects who have discontinued study treatment after achieving maximum clinical benefit as specified in Section 3.1.4.1 must continue imaging every 12 weeks, and the investigator must ensure close monitoring of symptoms and complete safety follow up as indicated for AEs.

• If progression occurs ≤ 52 weeks after last dose of study treatment, subjects have the option to re-initiate treatment with nivolumab monotherapy, or the combination of nivolumab with ipilimumab or with BMS-986016 (anti-LAG3) based on the initial cohort assignment, following new baseline assessments for eligibility.

The inclusion/exclusion criteria for re-initiation are described in Section 4.3.9. Re-initiation treatment schedules are described in Section 4.3.1 and Table 4.3.1-1. Time and events schedule of study assessments during re-initiation screening, during re-initiation treatment and during follow-up after re-initiation are included in Section 5.1

Treatment duration after re-initiation, inclusive of treatment beyond progression, will be for a maximum of 24 months.

[figure not shown]

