3.5 Discontinuation of Subjects from Treatment

Subjects MUST discontinue investigational product (and non-investigational product at the discretion of the investigator) for any of the following reasons:

- Subject's request to stop study treatment
- Any clinical adverse event (AE), laboratory abnormality or intercurrent illness which, in the opinion of the investigator, indicates that continued participation in the study is not in the best interest of the subject
- Termination of the study by Bristol-Myers Squibb (BMS)
- Loss of ability to freely provide consent through imprisonment or involuntarily incarceration for treatment of either a psychiatric or physical (eg, infectious disease) illness
- Any drug-related adverse event requiring discontinuation according to the management algorithms in the Appendix of the nivolumab IB.
- Additional protocol specified reasons for discontinuation (see Sections 3.1.4.1 and 4.3.6)

In the case of pregnancy, the investigator must immediately notify the BMS Medical Monitor/designee of this event. In most cases, the study drug will be permanently discontinued in an appropriate manner. If the investigator determines a possible favorable benefit/risk ratio that warrants continuation of study drug, a discussion between the investigator and the BMS Medical Monitor/designee must occur.

All subjects who discontinue investigational product should comply with protocol specified follow-up procedures as outlined in Section 5. The only exception to this requirement is when a subject withdraws consent for all study procedures including post-treatment study follow-up or loses the ability to consent freely (ie, is imprisoned or involuntarily incarcerated for the treatment of either a psychiatric or physical illness).

If study treatment is discontinued prior to the subject's completion of the study, the reason for the discontinuation must be documented in the subject's medical records and entered on the appropriate case report form (CRF) page.

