4.3.6 Discontinuation Criteria

Treatment with nivolumab, ipilimumab, and/or BMS-986016 should be permanently discontinued for the following:

- Any Grade 2 drug-related uveitis or eye pain or blurred vision that does not respond to topical therapy and does not improve to Grade 1 severity within the re-treatment period OR requires systemic treatment
- Any Grade 3 non-skin, drug-related adverse event lasting > 7 days, with the following exceptions for drug-related laboratory abnormalities, endocrinopathies, uveitis, pneumonitis, bronchospasm, diarrhea, colitis, neurologic toxicity, hypersensitivity reactions, and infusion reactions:
 - Grade 3 drug-related uveitis, pneumonitis, bronchospasm, diarrhea, colitis, neurologic toxicity, myocarditis, hypersensitivity reaction, or infusion reaction of any duration requires discontinuation
 - For Grade 3 endocrinopathy adverse events such as adrenal insufficiency, ACTH deficiency, hyper- or hypothyroidosis, or glucose intolerance, which resolve or are adequately controlled with physiologic hormone replacement (steroids, thyroid hormones) or glucose controlling agents, respectively, do not require treatment discontinuation
 - Grade 3 drug-related laboratory abnormalities do not require treatment discontinuation except:
 - ◆ Grade 3 drug-related thrombocytopenia > 7 days or associated with bleeding requires discontinuation
 - Any drug-related liver function test (LFT) abnormality that meets the following criteria require discontinuation:
 - \circ AST or ALT $> 8 \times ULN$

Protocol Amendment No: 09

Approved v1000 930073805 10.0

- o Total bilirubin > 5 x ULN
- o Concurrent AST or ALT > 3 x ULN and total bilirubin > 2 x ULN
- Any Grade 4 drug-related adverse event or laboratory abnormality (including but not limited to creatinine, AST, ALT, or Total Bilirubin), except for the following events which do not require discontinuation:
 - Grade 4 neutropenia \leq 7 days
 - Grade 4 lymphopenia or leukopenia
 - Grade 4 amylase or lipase abnormalities that are not associated with symptoms or clinical manifestations of pancreatitis.
 - Isolated Grade 4 electrolyte imbalances/abnormalities that are not associated with clinical sequelae and are corrected with supplementation/appropriate management within 72 hours of their onset

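### Cohort C6 (low severity): the delay list exempts some Grade 3 diarrhea for nivolumab that Section 4.3.6 makes a permanent stop, and Table 5.1-6 sets 21 days between 480 mg doses where Section 4.3 sets 25

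*Combined protocol and SAP*

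**What the plan says.** **Diarrhea.** Section 4.3.3 opens by applying the delay criteria to drug-related events "regardless of whether or not the event is attributed to nivolumab, ipilimumab, BMS-986016, daratumumab, or combinations". The C6 list is headed "Nivolumab and daratumumab (C6 Cohort treatment) administration should be delayed for the following", so it governs both drugs. One of its triggers is non-hematologic toxicity of Grade 3 or higher, with exceptions, and one exception is "Grade 3 diarrhea that responds to antidiarrheal treatment within 7 days".

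Section 4.3.6 begins "Treatment with nivolumab, ipilimumab, and/or BMS-986016 should be permanently discontinued for the following" and excludes no cohort. Within that list: "Grade 3 drug-related uveitis, pneumonitis, bronchospasm, diarrhea, colitis, neurologic toxicity, myocarditis, hypersensitivity reaction, or infusion reaction of any duration requires discontinuation". Section 3.5 lists the reasons for which a subject must come off investigational product, and one of them is "Additional protocol specified reasons for discontinuation (see Sections 3.1.4.1 and 4.3.6)". The C6 treatment section, 3.1.4.7, closes with "Please refer to Section 3.5 and Section 4.3.6 for reasons for discontinuation". Section 4.3.3 also leaves room to delay for "Any adverse event, laboratory abnormality, or intercurrent illness which, in the judgment of the investigator, warrants delaying the dose of study medication".

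**Interval.** Table 4.3-6 puts C6 nivolumab on 480 mg every four weeks from Week 25. The drug-dispensing row of Table 5.1-6 (the C6 schedule) sets a minimum of 21 days between those doses. Section 4.3 sets a minimum of 25 days for four-weekly nivolumab cycles.

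**The concern.** A delay exemption has no meaning for a drug that the same event stops for good. As written, the C6 list tells a site that a certain Grade 3 diarrhea needs no nivolumab delay, while another section says that nivolumab must not be given again if the event is related to it. The C6 line is also more lenient than the other nivolumab combinations in the same section. Nivolumab plus ipilimumab is delayed for non-skin drug-related events from Grade 2 (with limited exceptions), and C5 is delayed for diarrhea or colitis from Grade 2. At stake is a subject's safety if a site acts on the delay list alone.

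For the interval, a 480 mg dose given 21 to 24 days after the previous one complies with Table 5.1-6 and breaches Section 4.3. Sites, monitors and whoever classifies protocol deviations could reach different answers about the same dose.

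**Working it through.** No sample size, power or error rate is involved. The check sets the rules side by side and does a little interval arithmetic.

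**1. Diarrhea, by attribution.** The event is drug-related Grade 3 diarrhea that settles on antidiarrheals within 7 days.

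| Attributed to | Section 4.3.3, C6 list | Section 4.3.6 | Result for nivolumab |
|---|---|---|---|
| Nivolumab, or both drugs | No delay of either drug | Nivolumab stops permanently | The exemption has no valid use |
| Cannot be determined | No delay of either drug | All study drugs stop | The exemption has no valid use |
| Daratumumab only | No delay of either drug | Each drug assessed separately; nivolumab may continue | The exemption can operate |

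So the exemption is usable only for events put down to daratumumab alone. The list does not say so, and its opening sentence makes attribution irrelevant.

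The neighboring exceptions do not have this problem. Section 4.3.6 has a general rule that stops nivolumab for Grade 3 non-skin drug-related events lasting more than 7 days. The 7-day exceptions for nausea and vomiting sit comfortably beside it. Diarrhea is taken out of that general rule and put under the any-duration rule, so the same 7-day exception fails for it.

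**2. Interval.** Inputs: 28-day cycle (Table 4.3-6), 21 days (Table 5.1-6), 25 days (Section 4.3), visit window ±2 days (Table 5.1-6).

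- Earliest dose under Table 5.1-6: 28 − 21 = 7 days early.
- Earliest dose under Section 4.3: 28 − 25 = 3 days early.
- Gap between the rules: 25 − 21 = 4 days.
- Shortest interval if the ±2 days is taken around fixed calendar dates: 28 − 2 − 2 = 24 days, which is 1 day under 25.
- Shortest interval if the ±2 days is counted from the previous dose: 28 − 2 = 26 days, which is not under 25.

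The protocol does not say which way the window runs for C6, so both are shown. They describe doses given on schedule. If one dose is given late and the site then returns to the original calendar (an assumption), the next interval is 28 minus the delay. A delay of 4 to 7 days gives 24 to 21 days, which is where the two rules part.

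**3. Dose rate, as a check on harm.** Weekly dose = 480 / interval × 7.

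- 21 days: 480 / 21 × 7 = 160.0 mg/week.
- 25 days: 480 / 25 × 7 = 134.4 mg/week.
- 28 days: 480 / 28 × 7 = 120.0 mg/week.
- Reference regimen that Section 1.1.4.9 calls well tolerated, 10 mg/kg every two weeks, at that section's median weight of about 80 kg: 10 × 80 / 2 = 400 mg/week.

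All three rates are well under the reference.

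**The case against.** The strongest reply on diarrhea is that the two sections do different jobs. Section 4.3.3 says when a dose must wait; Section 4.3.6 says when a drug ends. Not requiring a delay does not permit continuing a drug that another rule stops. Section 3.5 makes the Section 4.3.6 reasons mandatory, Section 3.1.4.7 sends C6 sites there, unclear attribution stops everything, and investigators may always delay or discontinue on judgment. The visible text of the gastrointestinal algorithm in Appendix 1 also tells sites to rule out non-inflammatory causes and, where one is found, to treat it and continue therapy; diarrhea that settles on antidiarrheals could fit that route. (The flow chart itself is not legible in the copy available, so the rest of the algorithm could not be weighed.)

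Most of this stands. A reader might infer that the protocol sanctions further nivolumab after related Grade 3 diarrhea, or that a site cannot satisfy both rules. The documents support neither: a site can stop nivolumab under Section 4.3.6 without breaching Section 4.3.3. What remains is that the delay list, read alone, names nivolumab in an exemption it can rarely use and carries no pointer to the rule that overrides it.

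A reader might also infer that, after diarrhea due to daratumumab alone, nivolumab must wait until the diarrhea is back to baseline, because Section 4.3.5 requires that before treatment resumes. The text does not clearly require it. The resume condition in Section 4.3.6 applies once a discontinuation criterion has been met. The daratumumab stopping list names only infusion reactions, apart from investigator judgment. An exempt event also causes no delay from which to resume.

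On the interval, the 25-day sentence sits among text on nivolumab with ipilimumab and comes before the C6 dosing table. The other schedule tables that say 25 (5.1-2, 5.1-3, 5.1-9 and 5.1-10) belong to Arms N and N+I. A case can be made that Table 5.1-6 is the specific C6 rule. But the sentence is worded for four-weekly nivolumab cycles in general, C6 is on such a cycle from Week 25, and nothing in the protocol gives a reason for a shorter minimum in C6.

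**Conclusion.** Both mismatches are in the current operative text and should be corrected, at low severity.

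For diarrhea, the stricter rule governs any site that follows the cross-references. The residual risk is a site that relies on the delay list alone. The documents give no Grade 3 diarrhea rate for this combination and do not say how many C6 subjects were still being dosed at this amendment. The number affected therefore lies somewhere between 0 and the 40 planned, which is not an estimate.

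For the interval, the rules differ by 4 days as worded. For doses given within the visit window the practical difference is 0 to 1 day; it can reach the full 4 days only after a delayed dose. A reader might infer overexposure at 21 days. The dose-rate comparison does not support that, and it rests on the 80 kg median weight and on dose rate as a rough stand-in for exposure. The gain is one minimum interval for dosing and for classifying deviations.

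Neither point changes the C6 sample size, the definition of ORR or its confidence interval.

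**What to change.** 1. In the C6 list of Section 4.3.3, limit the diarrhea exemption to daratumumab dosing and add that nivolumab follows Section 4.3.6, including its drug-by-drug assessment. Do not add a requirement that diarrhea due to daratumumab alone resolve to baseline; that would be a new restriction, not a reconciliation of existing text.
2. In Table 5.1-6, change the minimum interval between 480 mg nivolumab doses from 21 to 25 days.

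The cost is two short text edits, by administrative letter or in the next amendment, and a notice to C6 sites. There is no statistical cost. If no C6 subject is still on treatment, the benefit is confined to a consistent record and to how past doses are classified.

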4.3.5 Criteria to Resume Treatment

Subjects may resume treatment with study drug when the drug-related AE(s) resolve to Grade ≤ 1 or baseline value, with the following exceptions:

- Subjects may resume treatment in the presence of Grade 2 fatigue
- Subjects who have not experienced a Grade 3 drug-related skin AE may resume treatment in the presence of Grade 2 skin toxicity
- Subjects with baseline Grade 1 AST/ALT or total bilirubin who require dose delays for reasons other than a 2-grade shift in AST/ALT or total bilirubin may resume treatment in the presence of Grade 2 AST/ALT OR total bilirubin. Subjects with combined Grade 2 AST/ALT AND total bilirubin values meeting discontinuation parameters (Section 4.3.6) should have treatment permanently discontinued
- Drug-related pulmonary toxicity, diarrhea, or colitis, must have resolved to baseline before treatment is resumed
- Drug-related endocrinopathies adequately controlled with only physiologic hormone replacement may resume treatment
- Subjects in the C5 Cohort may resume treatment with BMS-986016 when troponin levels return to normal

In the case of prior SARS-CoV-2 infection, symptoms should have resolved in order to resume study treatment and there should be no sequelae that would place the participant at a higher risk of receiving study intervention.

If the criteria to resume treatment are met, the subject should restart treatment at the next scheduled time point per protocol. However, if the treatment is delayed past the scheduled time point per protocol, the scheduled study treatment administration will be delayed, but not skipped, until

dosing resumes. In particular, this is to ensure that subjects in Arm N+I will receive 4 administrations of combined nivolumab and ipilimumab treatment if toxicity allows.

If dose delay is necessary for subjects in Arm N+I during Week 1-12 and for subjects in Cohort C3, both nivolumab and ipilimumab must be delayed until treatment can resume. However, if a nivolumab-related infusion reaction prevents subsequent infusion of ipilimumab on the same day, the dose of ipilimumab should be replaced as soon as possible. In such instances, at least 19 days must elapse between the replacement dose of ipilimumab and the administration of the next dose of nivolumab combined with ipilimumab.

If treatment is delayed > 6 weeks from the last dose, the subject must be permanently discontinued from study therapy, except as specified in Section 4.3.6.

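### In Cohort C6, once the last daratumumab dose was at Week 25 or later, a drug-related hold without a prolonged steroid taper falls under two delay rules that give opposite answers

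*Combined protocol and SAP*

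**What the plan says.** Two sets of rules apply to a toxicity hold in Cohort C6.

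**The 6-week limit.** Section 3.1.4.7, the C6 treatment section, uses the sentence that also stands in other cohorts' sections: "Study drug dosing may be delayed for toxicity for up to 6 weeks from the last dose". Section 4.3.3 opens with criteria for related events under any study drug, daratumumab included. It says "All study drugs must be delayed until treatment can resume" and "Treatment delays up to 6 weeks from the last dose are allowable". Section 4.3.5 adds the consequence: "If treatment is delayed > 6 weeks from the last dose, the subject must be permanently discontinued from study therapy". It leaves room for the cases listed in Section 4.3.6, which allows longer interruptions for prolonged steroid tapers and, with the medical monitor's approval, for reasons unrelated to study drug.

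**The daratumumab rules.** Section 4.3.3 and Table 4.3.3-1 skip a dose that falls outside its window. In the row for Week 25 onward the window is 21 days, and restart is at the "next planned every 4 weeks dosing date". The closing paragraph of Section 4.3.5 repeats, for Cohort 6, that a missed dose is followed by resumption at the next scheduled date. A separate sentence in Section 4.3.3 sets the stopping point: a related event that "requires a dose hold of more than 3 consecutive planned doses will result in permanent discontinuation of daratumumab".

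The text before the table words the 21-day allowance differently: "From Week 25 and beyond, the first dose (Week 25) can be delayed 21 days".

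**The concern.** Both sets of rules are in force for the same subject, and after Week 25 the dosing interval is long enough for them to collide. Under the table, a subject whose dose was skipped once for toxicity restarts. Under Section 4.3.5, the same subject has passed 6 weeks and must stop study therapy for good. No section states precedence.

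The collision is not confined to daratumumab. Nivolumab is also given every 4 weeks from Week 25 (Table 4.3-6), and Section 4.3.3 holds all study drugs together. A joint hold can therefore take nivolumab past its own limit in Section 4.3.6 while the table still plans a daratumumab restart.

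At stake are discontinuation decisions for individual subjects, and treatment duration and discontinuation counts in C6 that may depend on which section a site followed.

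**Working it through.** The plan states no figure to reproduce; the check is calendar arithmetic.

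**Inputs**
- Daratumumab interval: 7 days in Weeks 1–8, 14 days in Weeks 9–24, 28 days from Week 25 (Table 4.3-6). Planned doses fall at Weeks 1 to 8, then 9, 11, … 23, then 25, 29, 33, …
- Late window: 3 days, 7 days and 21 days in the three phases (Section 4.3.3 and Table 4.3.3-1).
- Consecutive doses that may be held for a daratumumab-related event: 3 (Section 4.3.3).
- Limit: 6 × 7 = 42 days from the last dose (Sections 3.1.4.7, 4.3.3, 4.3.5).

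**Formulas**
- Latest in-window gap = interval to the next dose + its window.
- Restart gap after k skips = date of the planned dose that follows the skipped ones − date of the last dose. Within one phase this is interval × (k + 1).

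**Last dose at Week 25 or later**
- In window: 28 + 21 = 49 days, 7 over the limit.
- One skip: 28 × 2 = 56 days, 14 over.
- Two skips: 28 × 3 = 84 days, 42 over.
- Three skips: 28 × 4 = 112 days, 70 over.

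A dose is not skipped until 49 days have passed, so in this period the restart row cannot operate without the 42-day limit already being exceeded.

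**All phases (days from last dose; bold exceeds 42)**

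| Last dose | Latest in window | 1 skip | 2 skips | 3 skips |
|---|---|---|---|---|
| Weeks 1–7 | 10 | 14 | 21–28 | 28–42 |
| Week 8 | 14 | 21 | 35 | **49** |
| Weeks 9–17 | 21 | 28 | 42 | **56** |
| Week 19 | 21 | 28 | 42 | **70** |
| Week 21 | 21 | 28 | **56** | **84** |
| Week 23 | 35 | 42 | **70** | **98** |
| Week 25 or later | **49** | **56** | **84** | **112** |

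Before Week 25 a breach needs two or three consecutive skips. A last dose at Week 23, a skipped Week 25 dose and a restart at Week 29 give 6 weeks exactly, which is not more than 6 weeks.

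**Do the exceptions resolve it?** The two in Section 4.3.6 cover a prolonged steroid taper and an approved reason unrelated to study drug. Grade 4 hematologic toxicity other than lymphopenia is a listed C6 delay trigger; if drug-related and held without a steroid taper, it meets neither exception.

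**Does the limit reach daratumumab?** Sections 3.1.4.7, 4.3.3 and 4.3.5 do not exclude it. In Section 4.3.6 the item on interruptions beyond 6 weeks sits in a list headed for nivolumab, ipilimumab and/or BMS-986016, and the separate daratumumab list has no counterpart. Section 4.3.6 also assesses discontinuation drug by drug for the C6 combination, whereas Section 4.3.3 delays all drugs together and Section 4.3.5 ends study therapy as a whole. The text supports either answer.

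**The 21-day allowance.** If it belongs only to the Week 25 dose, as the prose says, the gap from Week 23 is 14 + 21 = 35 days, inside the limit, and the 49-day figure falls away. The 56-day restart after one skip of a later dose remains on either reading.

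**The case against.** The best defence is that the rules are cumulative: the 6-week limit decides whether a restart is allowed, and the table only decides its date. The Week 25+ row would still serve steroid tapers and approved non-drug-related interruptions. A second defence is that the drug-specific text governs daratumumab: the closing paragraph of Section 4.3.5, the heading in Section 4.3.6, the drug-by-drug assessment there, and the statement in Section 4.3.3 that subjects withdrawn from daratumumab may stay on nivolumab. Section 4.3.6 also lets the sponsor and investigator consider re-initiation case by case after discontinuation, which softens the finality.

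Each reading is possible, but they lead to opposite actions and the protocol does not choose between them. On the cumulative reading, part of the tolerance for three held doses could not be used for such a hold from Week 25. On the drug-specific reading, the C6 sentence in Section 3.1.4.7 would not mean what it says for daratumumab.

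The objection that the effect is limited stands. Objective response rate is computed on all treated subjects, best overall response runs to progression or subsequent therapy rather than to the end of treatment (Section 8.3.1), and imaging continues after a stop without progression, unless outside systemic cancer treatment begins (Section 3.1.9.1). That sites actually diverged is not documented.

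**Conclusion.** The contradiction is real but bounded. It holds for a drug-related toxicity hold in C6, without a prolonged steroid taper, when the last daratumumab dose was at Week 25 or later. The excess over 42 days is 7 days for a dose at the end of its window (on the table's reading), 14 after one skip and 70 after three. Runs of skipped doses that begin earlier also exceed the limit, in the combinations tabulated above.

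A reader might infer more, and the documents do not support it:
- that the table itself plans restarts at 7 to 16 weeks: 7 weeks is a late dose, 16 weeks comes from the separate three-dose rule, and only the Week 25+ row conflicts after a single skip;
- that three sections require discontinuation: only Section 4.3.5 does, while Sections 3.1.4.7 and 4.3.3 state the allowable delay;
- that any skip from Week 25 is a breach: skipping the Week 25 dose alone is not;
- that the primary analysis is undermined: the direct effect is on descriptive exposure and discontinuation data.

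The result assumes that the last dose was on schedule, that the limit is counted from the last dose to the next, and that restart falls on the planned date. About 40 subjects are planned for C6; how many were still on treatment at Week 25, or had such a hold, is not given. The point should be corrected.

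**What to change.** Reconcile Section 3.1.4.7, Section 4.3.3 with Table 4.3.3-1, Section 4.3.5 and Section 4.3.6 so that they give one answer for C6. The text should state:
- whether the 6-week limit applies to daratumumab;
- whether it runs per drug or for the regimen, given that the drugs are held together but assessed separately for discontinuation;
- which rule prevails when the limit and the held-dose rule differ, with both expressed in days from the last dose for the weekly, 2-weekly and 4-weekly phases.

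Reconcile the Week 25 sentence with the Week 25+ row as well. Which delay rule should govern is a clinical decision for the sponsor, and this review does not choose one.

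The cost is one table and a few sentences in an amendment, with no added visits or subjects.
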